4.6.5.1.2. Pancreatitis Events

The counts and percentages of participants with pancreatitis will be presented for both investigator-reported events and subsequently confirmed adjudicated events. Detailed searching criteria can be found in Appendix 7 (Section 6.7).

Treatment-emergent, adjudication-confirmed pancreatitis will be considered as an AESI. Listings of participants with adjudicated pancreatitis may be provided if deemed necessary.

4.6.5.2. Gastrointestinal Adverse Events

4.6.5.2.1. Nausea, Vomiting, and Diarrhea

Summaries and analyses for the incidence and severity of nausea, vomiting (including “vomiting” and “vomiting projectile”), diarrhoea (including “diarrhea” and “diarrhoea”), and the

3 events combined will be provided by each treatment group. A summary of the prevalence over time for nausea, vomiting, and diarrhea will also be presented. Time to the first onset of nausea, vomiting, and diarrhea will be plotted.

4.6.5.2.2. Severe Gastrointestinal Events

Severe gastrointestinal (GI) AEs (GI SOC) will be captured with the AE-CRF form, and serious cases will be captured with the SAE form. The PTs in the GI SOC from the most recent MedDRA version at the time of DBL will be used to identify GI AEs, and only the PTs with severe/serious cases will be considered AESI.

The counts and percentages of participants with severe/serious GI events will be summarized by treatment.

4.6.5.3. Hepatobiliary Disorders

4.6.5.3.1. Hepatic Events

The counts and percentages of participants with treatment-emergent, potentially drug-related hepatic events will be summarized by treatment using MedDRA PTs. Detailed searching criteria can be found in Appendix 7 (Section 6.7). Severe/serious hepatic events will be considered AESI and summarized separately.

4.6.5.3.2. Acute Gallbladder Disease

Events related to acute gallbladder disease will also be summarized by treatment groups by PTs with decreasing frequency. Detailed searching criteria can be found in Appendix 7 (Section 6.7).

Severe/serious acute gallbladder disease will be considered AESI and summarized separately.

4.6.5.3.3. Liver Enzymes

Common analyses for laboratory analyte measurements described in Section 4.6.3.6 are applicable for the liver-enzyme-related measurements. This section provides additional analyses for liver enzymes.

The counts and percentages of participants with the following elevations in hepatic laboratory tests at any time during the treatment period, and during the entire study including the follow-up period, will be summarized between treatment groups:

- The counts and percentages of participants with an alanine aminotransferase (ALT) measurement ≥ 3 times ($3\times$), 5 times ($5\times$), and 10 times ($10\times$) the central lab ULN will be summarized for all participants with a postbaseline value and for subsets based on various levels of baseline value:
 - participants whose nonmissing maximum baseline value is $\leq 1 \times$ ULN
 - participants whose maximum baseline is $>1 \times$ ULN, and
 - participants whose baseline values are missing.
- The counts and percentages of participants with an aspartate aminotransferase measurement $\geq 3 \times$, $5 \times$, and $10 \times$ the central lab ULN will be summarized for all participants with a postbaseline value and for subsets based on various levels of baseline values, as described above for ALT.

- The counts and percentages of participants with a total bilirubin (TBL) measurement $\geq 2 \times$ the central lab ULN will be summarized for all participants with a postbaseline value and for subsets based on various levels of baseline values:
 - participants whose nonmissing maximum baseline value is $\leq 1 \times$ ULN
 - participants whose maximum baseline is $>1 \times$ ULN, but $<2 \times$ ULN
 - participants whose maximum baseline value is $\geq 2 \times$ ULN, and
 - participants whose baseline values are missing.
- The counts and percentages of participants with a serum alkaline phosphatase measurement $\geq 2 \times$ the central lab ULN will be summarized for all participants with a postbaseline value and for subsets based on various levels of baseline values, as described above for TBL.

Maximum baseline will be the maximum nonmissing observation in the baseline period. The maximum postbaseline value will be the maximum nonmissing value from the postbaseline period. Planned and unplanned measurements will be included.

4.6.5.4. Hypoglycemia

The following categories in accordance with the 2020 American Diabetes Association position statement on glycemic targets (ADA 2020) will be defined in the database.

Glucose Alert Value (Level 1)

- **Documented symptomatic hypoglycemia** is defined as any time a participant feels that he/she is experiencing symptoms and/or signs associated with hypoglycemia and has a blood glucose (BG) level of <70 mg/dL (<3.9 mmol/L).
- **Documented asymptomatic hypoglycemia** is defined as any event not accompanied by typical symptoms of hypoglycemia but with a measured BG <70 mg/dL (<3.9 mmol/L).
- **Documented unspecified hypoglycemia** is defined as any event with no information about symptoms of hypoglycemia available but with a measured BG <70 mg/dL (<3.9 mmol/L).

Documented Clinically Significant Hypoglycemia (Level 2)

- **Documented symptomatic hypoglycemia** is defined as any time a participant feels that he/she is experiencing symptoms and/or signs associated with hypoglycemia and has a BG level of <54 mg/dL (<3.0 mmol/L).
- **Documented asymptomatic hypoglycemia** is defined as any event not accompanied by typical symptoms of hypoglycemia but with a measured BG <54 mg/dL (<3.0 mmol/L).
- **Documented unspecified hypoglycemia** is defined as any event with no information about symptoms of hypoglycemia available but with a measured BG <54 mg/dL (<3.0 mmol/L).

Severe Hypoglycemia (Level 3)

- **Severe hypoglycemia** is defined as an episode with severe cognitive impairment requiring the assistance of another person to actively administer carbohydrate, glucagon, or other resuscitative actions. These episodes may be associated with sufficient neuroglycopenia to induce seizure or coma. Plasma glucose (PG) measurements may not be available during such an event, but neurological recovery attributable to the restoration of PG to normal is considered sufficient evidence that the event was induced by a low PG concentration.

Other Hypoglycemia Categories

- **Nocturnal hypoglycemia** is defined as any hypoglycemic event that occurs between bedtime and waking.

To avoid duplicate reporting, all consecutive hypoglycemic events occurring within a 1-hour period will be considered to be a single hypoglycemic event.

Both the incidence (percentage of participants experiencing ≥ 1 episode) and the rate (episodes/participant/year) of Level 2 or Level 3 hypoglycemia, and Level 3 hypoglycemia, will be reported.

[figure not shown]
If a hypoglycemic event meets the criteria of severe, the event would specifically be collected as an SAE. Serious hypoglycemia is defined by pharmacovigilance criteria and will also be captured with an SAE form.

Severe/serious hypoglycemia will be considered AESI. The summaries of severe/serious hypoglycemia will be provided by treatment group. A listing of all events of severe/serious hypoglycemia may be provided, if deemed necessary. This listing will provide treatment allocation and clinical characteristics of the hypoglycemic event.

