### 8.3.2. Special Safety Topics

#### 8.3.2.1. Hypoglycemia

Upon ICF signing, all participants will be educated about signs and symptoms of hypoglycemia, how to treat hypoglycemia, and how to collect appropriate information for each episode of hypoglycemia.

Hypoglycemia may be identified by spontaneous reporting of symptoms from participants (whether confirmed or unconfirmed by simultaneous glucose values) or by blood glucose (BG) samples collected during study visits.

All participants who develop diabetes during the study will be provided with glucometers. Participants without diabetes may be given glucometers to assist in the evaluation of reported symptoms consistent with hypoglycemia at the investigator's discretion. Participants receiving glucometers will be provided a diary to record relevant information (for example, glucose values, symptoms).

All hypoglycemic episodes will be recorded on a specific eCRF (Hypoglycemic Events eCRF) and should not be recorded on the AE eCRF, unless the event meets serious criteria. If a hypoglycemic event meets severe criteria (see definition below), it should be recorded as serious on the AE and SAE eCRFs, and reported to Lilly as an SAE. All hypoglycemic events collected on the hypoglycemic eCRF will be considered as treatment-emergent (TE) and included in the analysis of incidence and rate of hypoglycemic events.

Investigators should use the following definitions and criteria when diagnosing and categorizing an episode considered to be related to hypoglycemia (the BG values in this section refer to values determined by a laboratory or International Federation of Clinical Chemistry and Laboratory Medicine blood-equivalent glucose meters and strips) in accordance with the 2020 American Diabetes Association position statement on glycemic targets (ADA 2020):

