4.6.2. Adverse Events

4.6.2.1. Treatment-Emergent Adverse Events

A treatment-emergent adverse event (TEAE) is defined as an event that first occurred, or worsened in severity, after baseline (defined in [Table GPHM.4.1](#)). The Medical Dictionary for Regulatory Activities (MedDRA) Lowest-Level Term (LLT) will be used in the treatment-emergent derivation. The maximum severity for each LLT during the baseline period, including ongoing medical history, will be used as baseline severity. Events with a missing severity during the baseline period will be treated as “mild” in severity for determining treatment-emergence. Events with a missing severity during the postbaseline period will be treated as “severe”, and treatment-emergence will be determined by comparing to baseline severity.

For events occurring on the day of first taking study medication, the information collected in the case report form (CRF) (for example, treatment-emergent flag, start time of study treatment and event) will be used to determine whether the event was pre- or posttreatment. If the relevant information is not available, then the events will be counted as posttreatment.

In an overview table, the counts and percentages of participants who experienced a TEAE, serious adverse event (SAE), death, or discontinued from study and/or study treatment due to an adverse event (AE) will be summarized by treatment.

The counts and percentages of participants with TEAEs will be summarized by treatment using MedDRA Preferred Terms (PTs) nested within System Organ Class (SOC). Events will be ordered by decreasing frequency within SOC. System Organ Classes will be presented in alphabetical order. Statistical comparisons will be applied at both the SOC and PT levels. If necessary, the percentages of participants with TEAEs will also be summarized by treatment using MedDRA PT (without regard to SOC) by decreasing frequency.

The counts and percentages of participants with TEAEs will be summarized by maximum severity and treatment using MedDRA PTs. For each participant and TEAE, the maximum severity for the MedDRA PT is the maximum postbaseline severity observed from all associated LLTs mapping to the MedDRA PT. Maximum severity will be determined based on the nonmissing severities. If all severities are missing for the defined postbaseline period of interest, it will show as missing in the table.

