4.6.5. Special Safety Topics

For AEs of special interest (AESI) or special safety topics, the counts and percentages of participants will be summarized by treatment and PT with decreasing frequency. Individual participant-level data may be presented. Displays with individual participant-level data may be created using various formats, such as a customized listing and/or a customized graphical patient profile. Adverse events of special interest are defined in each section of special safety topics, where applicable.

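### The SAP's hypoglycemia incidence and rate analysis leaves out nonserious episodes (glucose 54 to <70 mg/dL, or symptomatic with no glucose value) that the protocol says it includes

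*SAP*

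**What the plan says.** Protocol Section 8.3.2.1 sends every hypoglycemic episode, of any level, to a Hypoglycemic Events eCRF. These episodes "should not be recorded on the AE eCRF, unless the event meets serious criteria". The same section treats all events on that eCRF as treatment-emergent and says they are "included in the analysis of incidence and rate of hypoglycemic events". It sets no restriction by level. It also accepts episodes identified from reported symptoms alone, with or without a glucose value at the time.

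Both documents define Level 1 as blood glucose below 70 mg/dL (3.9 mmol/L), Level 2 as below 54 mg/dL (3.0 mmol/L), and Level 3 as an episode with severe cognitive impairment that needs another person's help. SAP Section 4.6.5.4 says that these categories "will be defined in the database". For analysis it commits to the incidence and "the rate (episodes/participant/year) of Level 2 or Level 3 hypoglycemia, and Level 3 hypoglycemia, will be reported". It then adds: "Severe/serious hypoglycemia will be considered AESI", with summaries by treatment group and an optional listing.

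**The concern.** The protocol takes nonserious hypoglycemia out of ordinary adverse event reporting and assigns it to a dedicated incidence and rate analysis. The SAP's version of that analysis drops part of what was assigned to it. Level 1 is defined, but no planned output uses it.

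What is at stake is completeness of descriptive safety reporting. Hypoglycemia is a special safety topic in the protocol. Participants are advised to keep a deficit of about 500 kcal/day after randomization, and those who develop diabetes may start glucose-lowering medication (Protocol Sections 5.3.1 and 6.5). A reader of the study report would expect the hypoglycemia table to cover what the protocol said it would cover.

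**Working it through.** There is no stated figure to reproduce. The check sets the two texts side by side.

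**Step 1: the glucose band.** Level 1 is <70 mg/dL and Level 2 is <54 mg/dL. Level 1 without Level 2 is therefore 54 to <70 mg/dL (3.0 to <3.9 mmol/L).

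**Step 2: follow each type of episode through both documents.** The protocol requires a Level 3 episode to be recorded as serious.

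| Episode | Hypoglycemia eCRF | AE eCRF | SAP incidence and rate | SAP severe/serious summary |
|---|---|---|---|---|
| Level 3 | yes | yes | yes | yes |
| Nonserious, glucose <54 mg/dL | yes | no | yes | no |
| Serious, glucose 54 to <70 mg/dL, not Level 3 | yes | yes | no | yes |
| Nonserious, glucose 54 to <70 mg/dL | yes | no | **no** | **no** |
| Nonserious, symptomatic, no glucose value, not Level 3 | yes | no | **no** | **no** |

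The protocol's sentence covers all five rows. The SAP's incidence and rate cover the first two, and its severe/serious summary picks up the third. The last two rows have neither output. Levels 1 and 2 both require a glucose value, so the episodes in the last row fit no SAP level at all.

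**Step 3: look for another output that covers the last two rows.**
- SAP 4.6.2.1 tabulates treatment-emergent adverse events as participant counts by Preferred Term. The SAP does not say whether hypoglycemia eCRF episodes feed these tables. If they did, the tables would show neither a rate nor a glucose level.
- The default for special topics in SAP 4.6.5 has the same limit: "the counts and percentages of participants will be summarized by treatment and PT with decreasing frequency".
- Glucose is in the central chemistry panel. Protocol 9.4.4.4.4 plans percentages of participants with treatment-emergent low laboratory values, and SAP 4.6.3.6 plans low/normal/high shift tables by arm. These give some information on low glucose by arm. They classify participants by laboratory limits; they do not count eCRF episodes or give a rate.

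**Step 4: look for a recorded reason.** Protocol 9.4.1 asks that a change in analysis methods short of a principal feature be described and justified in the SAP or the study report. SAP 4.6.5.4 gives no reason for the narrower scope. SAP 4.9 lists a ≥20% weight-reduction objective, non-HDL cholesterol and a region subgroup, and nothing on hypoglycemia.

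**The case against.** The best case for the SAP is that the protocol sentence is a data-capture rule. It stands in the safety procedures, not in the statistical section. It could mean only that eCRF events skip the usual treatment-emergence derivation and are the source for whatever analysis the SAP defines. The protocol's statistical section lists only severe hypoglycemia among events of special interest and leaves the details to the SAP, which goes further by including Level 2. Both documents label Level 2 as clinically significant and Level 1 as an alert value, so reporting Levels 2 and 3 in people without diabetes at entry is a defensible clinical choice. The SAP states its scope openly, keeps Level 1 in the database, and allows additional analyses.

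Much of this stands, and it keeps the priority low. It does not remove the conflict. The protocol sentence covers all eCRF events and names incidence and rate, and the list of events of special interest does not limit it. Permission to add an analysis is not a commitment to do so.

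The objection that detection is unsystematic is also sound: "Participants without diabetes may be given glucometers to assist in the evaluation of reported symptoms consistent with hypoglycemia", at the investigator's discretion. That argues for a descriptive row with a caveat. The same limit already applies to nonsevere Level 2 episodes, which the SAP does report.

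A reader might infer more than the documents support. They do not show that hypoglycemia data are being withheld, since the episodes are collected and the SAP's scope is stated. They do not show that low glucose goes unreported by arm, because the laboratory summaries cover part of it. Little can be read into the silence of SAP 4.9, whose list is introduced as changes to objectives; hypoglycemia is not an objective, and the study report remains a permitted place for the justification.

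**Conclusion.** The mismatch is real and minor. Nonserious episodes at 54 to <70 mg/dL, and nonserious symptomatic episodes with no glucose value that are not Level 3, have no planned incidence or rate, although the protocol says that all hypoglycemia eCRF events are in that analysis. This rests on reading the protocol sentence as written.

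The size can be given only as types of episode. Neither document states an expected frequency, so any count per arm would be a guess. Episodes below 54 mg/dL, Level 3 episodes and serious episodes are all reported, so nothing here suggests that a serious harm would be missed. No efficacy or type I error result changes.

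**What to change.** In SAP 4.6.5.4, add the incidence and the rate per participant-year of all hypoglycemia eCRF events, by arm on the Safety Analysis Set. A second row for episodes with glucose 54 to <70 mg/dL is optional. It cannot replace the first, because only the all-event row captures symptomatic episodes without a glucose value. Keep both rows descriptive with no between-arm test, and add a note that detection is unsystematic because glucometer use is discretionary in participants without diabetes.

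If the sponsor prefers the narrower scope, it should state and justify that in SAP 4.6.5.4 or 4.9. That would settle the documentation point but leave the episodes untabulated.

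The cost is a short addition to the SAP and one or two descriptive rows from data already collected. The drawback is that the rows cannot support between-arm inference, since detection could differ by arm, and they may be over-read if the note is dropped.

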4.6.5.5. Immunogenicity**4.6.5.5.1. Definitions of Sample ADA Status**

At a high level, an individual sample is potentially examined multiple times, in a hierarchical procedure, to produce a sample anti-drug antibodies (ADA) assay result, potentially multiple cross-reactive ADA assay results, and multiple neutralizing antibodies (NAb) assay results. The cut points used, the drug tolerance of each assay, and the possible values of titers are operating characteristics of the assay.

[Figure GPHM.4.1](#) details a flow chart that reflects the multitiered testing approach.

Abbreviations: ADA = anti-drug antibody; CP = cut point; GIPR = glucose-dependent insulinotropic polypeptide receptor; GLP-1R = glucagon-like peptide-1 receptor; LY = LY3298176 (tirzepatide); NAb = neutralizing antibody; nGIP = native glucose-dependent insulinotropic polypeptide receptor; nGLP-1 = native glucagon-like peptide-1.

Figure GPHM.4.1. Flowchart of immunogenicity multitiered testing approach.

Table GPHM.4.7 outlines results as reported from Tier 2a of the multitiered testing approach. Tier 4 results are reported similarly.

Table GPHM.4.7. Sample Anti-Drug Antibodies (ADA) Assay Results

Sample Laboratory Result	Explanation
Detected	ADA are detected and confirmed.
Not Detected	The raw result as reported from the laboratory indicates not detected. The clinical interpretation of such results depends on other factors (see Table GPHM.4.8).
NO TEST, QNS, etc.	Sample exists but was unevaluable by the assay.

Abbreviations: ADA = anti-drug antibodies; QNS = quantity not sufficient.

It can be the case that the presence of high concentrations of tirzepatide will affect ADA immunoassays, and conversely high levels of ADA may affect the measurement of tirzepatide concentration. Thus, a tirzepatide drug concentration, assessed from a sample drawn at the same time as the ADA sample, plays a key role in clinical interpretation of a sample when the laboratory result is Not Detected (see [Table GPHM.4.8](#)).

Table GPHM.4.8. Sample Clinical Anti-Drug Antibodies Interpretation Results

Sample Clinical Interpretation	Explanation
ADA Present	ADA assay result is Detected.
ADA Not Present	ADA assay result is Not Detected, and simultaneous drug concentration is at a level that has been demonstrated to not interfere in the ADA detection method (that is, drug concentration is below the assay's drug tolerance level). For participants receiving placebo, drug concentration is not assessed and is assumed to be below the assay's drug tolerance level. If drug concentration was planned but is not available for a treatment-period sample, a Not Detected sample will be declared ADA Not Present.
ADA Inconclusive	ADA assay result is Not Detected, but the drug concentration in the sample is greater than or equal to the assay's drug tolerance level, which may cause interference in the ADA detection method.

Abbreviations: ADA = antidrug antibodies.

All ADA-present samples will be evaluated for cross-reactivity to native glucose-dependent insulinotropic polypeptide (GIP) (Tier 2b), cross-reactivity to native glucagon-like peptide-1 (GLP-1) (Tier 2c), NAb tirzepatide on the GIPR receptor (GIPR) (Tier 4a), and NAb LY (tirzepatide) on the GLP-1 receptor (GLP-1R) (Tier 4b). If cross-reactive ADA against native GIP is detected, the *in silico* assessment for cross-reactive NAb against native GIP is evaluated. If cross-reactive ADA against GLP-1 is detected, the *in silico* assessment for cross-reactive NAb against native GLP-1 is evaluated ([Figure GPHM.4.1](#)).

Similar terminology to [Table GPHM.4.8](#) applies for each type of cross-reactive and NAb assay. Importantly, each of these is a distinct assay and, in general, has different assay operating characteristics.

The following are considered inconclusive for the NAb result:

- NAb tirzepatide on GIPR - If an NAb result is not detected and pharmacokinetic (PK) concentration is greater than or equal to the drug tolerance limit of the NAb tirzepatide on the GIPR assay.
- NAb tirzepatide on GLP-1R - If an NAb result is not detected and PK concentration is greater than or equal to the drug tolerance limit of the NAb tirzepatide on the GLP-1R assay.

An *in silico* method utilizing results from Tiers 2b and 2c, Tiers 4a and 4b, and tirzepatide concentrations is used to determine cross-reactive NAb against native GIP and GLP-1. The *in silico* method is outlined in [Table GPHM.4.9](#).

Table GPHM.4.9. *In Silico* Classification for Cross-Reactive NAb

In Silico Classification	Cross-Reactive ADA Result	NAb Result	Circulating Tirzepatide Level (ng/mL)	In Silico Cross-Reactive NAb Interpretation
Cross-Reactive	Tier 2b: Not Detected	Tier 4a: Not Detected or Detected or Tier 4a: Detected, NA, or Missing	Any value or missing	Not Present
NAb to nGIP	Tier 2b: Detected	Tier 4a: Not Detected	< drug tolerance limit of the assay	Not Present
	Tier 2b: Detected	Tier 4a: Not Detected	≥ drug tolerance limit of the assay	Inconclusive
	Tier 2b: Detected	Tier 4a: Detected	< drug tolerance limit of the assay	Present
	Tier 2b: Detected	Tier 4a: Detected	≥ drug tolerance limit of the assay	Present
Cross-Reactive	Tier 2c: Not Detected	Tier 4b: Not Detected or Detected or Tier 4b: Detected, NA, or Missing	Any value or missing	Not Present
NAb to nGLP-1	Tier 2c: Detected	Tier 4b: Not Detected	< drug tolerance limit of the assay	Not Present
	Tier 2c: Detected	Tier 4b: Not Detected	≥ drug tolerance limit of the assay	Inconclusive
	Tier 2c: Detected	Tier 4b: Detected	< drug tolerance limit of the assay	Present

In Silico Classification	Cross-Reactive ADA Result	NAb Result	Circulating Tirzepatide Level (ng/mL)	In Silico Cross- Reactive NAb Interpretation
	Tier 2c: Detected	Tier 4b: Detected	≥ drug tolerance limit of the assay	Present

Abbreviations: ADA = anti-drug antibodies; NA = not applicable; NAb = neutralizing antibody; nGIP = native glucose-dependent insulintropic polypeptide; nGLP-1 = native glucagon-like peptide-1; Tier 2b = cross-reactive ADA to nGIP; Tier 2c = cross-reactive ADA to nGLP-1; Tier 4a = NAb LY (tirzepatide) on GIPR; Tier 4b = NAb LY (tirzepatide) on GLP-1R.

Note that, in the case of an ADA Inconclusive sample, each of the NAb and Cross-Reactive NAb assay results are taken to be Inconclusive.

Note also that any reference to an assay cut point and/or drug tolerance is population specific and is subject to modification to study-specific parameters per regulatory guidance.

4.6.5.5.2. *Definitions of Immunogenicity Assessment Periods*

Immunogenicity Baseline Observations

The baseline period for immunogenicity assessment for each participant includes all observations prior to the first dose of study treatment. In instances where multiple baseline observations are collected, to determine participant ADA status, the last nonmissing immunogenicity assessment prior to first administration of study drug is used to determine treatment-emergent status (see below).

Immunogenicity Postbaseline Period Observations

Postbaseline period observations for each participant include all observations after the first administration of study drug. There are 2 different periods:

- The planned treatment period is defined as from the first dose of treatment to end of the treatment period.
- The entire postbaseline period is defined as from the first dose of treatment to the end of the safety follow-up visit or the date of study withdrawal.

4.6.5.5.3. *Definitions of Participant ADA Status*

Participants Evaluable for Treatment-Emergent ADA (TE ADA)

A participant is evaluable for TE ADA if the participant has a nonmissing baseline ADA result and at least 1 nonmissing postbaseline ADA result.

TE-ADA-Unevaluable Participants

A TE ADA-unevaluable participant is any participant who does not meet the evaluable criteria.

Baseline ADA Present (preexisting antibody)

Anti-drug antibodies are detected in a sample collected up to the first dose date and time.

Baseline ADA Not Present

Anti-drug antibodies are not detected, and the corresponding PK concentrations are missing or are below the drug tolerance limit in a sample collected up to the first dose date and time.

Treatment-Emergent ADA-Positive (TE ADA+) Participants

A participant who is evaluable for TE ADA is TE ADA+ if either of the following holds:

- The participant has baseline status of ADA Not Present and at least 1 postbaseline status of ADA Present with titer $\geq 2 \times$ the minimum required dilution (MRD) of the ADA assay.
- The participant has baseline and postbaseline status of ADA Present, with the postbaseline titer being 2 dilutions (4-fold) greater than the baseline titer. That is, the participant has a baseline status of ADA Present, with a titer of 1:baseline, and at least 1 postbaseline status of ADA Present, with a titer of 1:postbaseline, with postbaseline divided by baseline ≥ 4 .

As shown in [Figure GPHM.4.1](#), a titer is expected when an ADA assay result is Detected. On occasion, the corresponding assay cannot be performed, in which case a titer value will be imputed for the purpose of TE ADA determination. A baseline sample with detected ADA and no titer is imputed to be the MRD (1:10), and a postbaseline sample with ADA detected and no titer is imputed to be 1 dilution above the MRD (1:20).

Treatment-Emergent ADA-Inconclusive Participants

A participant who is evaluable for TE ADA is TE ADA Inconclusive if $\geq 20\%$ of the participant's postbaseline samples are ADA Inconclusive and all remaining postbaseline samples are ADA Not Present.

Treatment-Emergent ADA-Negative (TE ADA-) Participants

A participant who is evaluable for TE ADA is TE ADA- when the participant is not TE ADA+ and the participant is not TE ADA Inconclusive.

For each NAb assay, the following are defined:

- NAb-positive (NAb+) participant - A participant who is TE ADA+ and has an NAb positive sample in the postbaseline period.
- NAb-Inconclusive participant - A participant who is TE ADA+, is not NAb+, and all samples that have TE ADA+ titer have an NAb Inconclusive sample result.
- NAb-negative (NAb-) participant - A participant is NAb- when the participant is neither NAb+ nor NAb Inconclusive.

Unless specified otherwise, the above-mentioned definitions of NAb are applicable to all NAb analyses, including cross-reactive NAb analyses and cross-reactive antibodies.

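### SAP Table GPHM.4.9 labels an ADA-present sample cross-reactive NAb Not Present even when tirzepatide is at or above the cross-reactive assay's own drug tolerance limit, where the SAP's general rule gives Inconclusive.

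*SAP*

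**What the plan says.** SAP Section 4.6.5.5.1 starts from drug interference: "It can be the case that the presence of high concentrations of tirzepatide will affect ADA immunoassays". Table GPHM.4.8 therefore reads a Not Detected ADA result together with the drug level in the same sample:

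- Drug below the assay's tolerance: Not Present.
- Drug planned but unavailable for a treatment-period sample: Not Present.
- Inconclusive when "the drug concentration in the sample is greater than or equal to the assay's drug tolerance level, which may cause interference in the ADA detection".

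The section then says that similar terminology "applies for each type of cross-reactive and NAb assay", and that these are distinct assays which in general have different operating characteristics. ADA-present samples go on to Tier 2b (cross-reactivity to native GIP), Tier 2c (native GLP-1), and Tiers 4a and 4b (neutralization of tirzepatide on the GIP and GLP-1 receptors).

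Table GPHM.4.9 combines these results. Its first row in the native GIP block is "Tier 2b: Not Detected", and in the native GLP-1 block "Tier 2c: Not Detected". Both rows accept every Tier 4 outcome, carry the drug level "Any value or missing", and end in Not Present. Drug level changes the label only when Tier 2b/2c is Detected and Tier 4a/4b is Not Detected; there, "≥ drug tolerance limit of the assay" gives Inconclusive. A note under the table adds that "in the case of an ADA Inconclusive sample, each of the NAb and Cross-Reactive NAb assay results are taken to be Inconclusive".

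**The concern.** A Not Detected result from an assay that drug can mask is not evidence of absence, and the SAP says so for ADA. Table GPHM.4.9 does not carry that through from Tier 2b/2c. One sample can be Inconclusive for cross-reactive ADA under the general rule and Not Present for the cross-reactive NAb derived from that same result.

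The label feeds the participant-level tables. Section 4.6.5.5.3 applies its NAb participant definitions to the cross-reactive analyses. A participant with treatment-emergent ADA (TE ADA+) who is not NAb+ is NAb-Inconclusive only if every sample with a TE ADA+ titer is Inconclusive; otherwise the participant is NAb-negative. Section 4.6.5.5.4 tabulates these classes and summarizes the in silico result. The present rule can only make the Inconclusive group look smaller and the negative group larger, so the tables would overstate how firmly cross-reactive NAb had been ruled out.

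**Working it through.** There is no figure to reproduce. The check sets the two rules side by side for an ADA-present sample with Tier 2b Not Detected. The native GLP-1 block is the same, with 2c for 2b and 4b for 4a.

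**Step 1. General rule against Table GPHM.4.9, by drug level**

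| Drug level against Tier 2b tolerance | Cross-reactive ADA by Table GPHM.4.8 logic | Cross-reactive NAb in Table GPHM.4.9 | Result |
|---|---|---|---|
| Below | Not Present | Not Present | Agree |
| Missing | Not Present | Not Present | Agree |
| At or above | Inconclusive | Not Present | Differ |

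**Step 2. When does the difference matter?** If drug may have masked Tier 2b, its true result could be either Detected or Not Detected. Table GPHM.4.9 gives the NAb label for each:

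| Tier 4a result (drug at or above Tier 2b tolerance) | Label if Tier 2b Not Detected | Label if Tier 2b Detected | Does Not Present stand? |
|---|---|---|---|
| Not Detected, drug below Tier 4a tolerance | Not Present | Not Present | Yes: Tier 2b makes no difference |
| Not Detected, drug at or above Tier 4a tolerance | Not Present | Inconclusive | No |
| Detected | Not Present | Present | No |
| NA or missing | Not Present | No row given | No |

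The second table reads the limit in the Tier 2b Detected rows as Tier 4a's, since the drug level there qualifies a Tier 4a Not Detected result. The SAP writes only "≥ drug tolerance limit of the assay" and does not name the assay.

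**Step 3. Does the note under the table close the gap?** No. It applies to samples that are ADA Inconclusive at Tier 2a. The disputed samples are ADA Present, because those are the ones sent to Tiers 2b and 2c.

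**Step 4. Size.** An affected sample must meet four conditions together:

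1. ADA detected at Tier 2a.
2. Tier 2b or 2c Not Detected.
3. Tirzepatide at or above that Tier 2 assay's tolerance.
4. No Tier 4a/4b Not Detected result with drug below the Tier 4 tolerance.

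The documents give no ADA rate, tolerance limit or tirzepatide concentration, so the count cannot be computed. It is zero if observed levels never reach the Tier 2b/2c tolerance. Placebo samples are outside the problem, because their drug level is assumed to be below tolerance.

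**Step 5. Direction.** Relabelling moves a sample from Not Present to Inconclusive and never to Present. A participant changes class only if all samples with a TE ADA+ titer become Inconclusive.

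**The case against.** The best defence is that the disputed row is a gate. Section 4.6.5.5.1 says the in silico assessment is evaluated when cross-reactive ADA is detected; without detection there is nothing to evaluate and Not Present is a default. The explicit Inconclusive bullets for NAb results name only the two Tier 4 assays, and the extension to Tier 2b/2c rests on the words about similar terminology. Detection at Tier 2a might also suggest that drug was not masking.

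Part of this stands: the extension is brief, and Figure GPHM.4.1, which might qualify it, was not available to me. But a gate that did not open explains why an assessment was not made; it does not turn a possibly masked result into a definite negative. Detection at Tier 2a shows only that Tier 2a was not fully masked, and the SAP says the assays differ.

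A reader might also infer stronger points, which the documents do not support:

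- *Missing drug levels are mishandled.* They are not: Table GPHM.4.8 makes Not Detected with a missing level Not Present, and Table GPHM.4.9 follows it.
- *Every Not Detected result at high drug should be Inconclusive.* That goes too far. With a valid Tier 4 negative, a sample Not Detected at Tier 2b would get a less negative label than one Detected there.
- *Tier 4 Detected beside Tier 2 Not Detected is contradictory in itself.* Tier 4 measures neutralization of tirzepatide, so antibody to the drug without cross-reactivity is a legitimate finding when the Tier 2 negative is valid.
- *Most on-drug samples are affected.* The Schedule of Activities puts 4 of 5 scheduled postbaseline immunogenicity samples (Weeks 4, 12, 24 and 72, but not Visit 801) on drug in a completer, which is 80%. That says nothing about how many meet the four conditions in the working.

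**Conclusion.** The concern holds in a limited form. For ADA-present samples with tirzepatide at or above the Tier 2b/2c tolerance and no valid Tier 4a/4b negative, the Not Present label conflicts with the SAP's own treatment of Not Detected results. Elsewhere in the disputed rows the label agrees with the general rule or can be supported.

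The size is unknown and may be zero. The effect is confined to descriptive immunogenicity tabulations, with no bearing on the primary or key secondary analyses. Nor do the documents rank cross-reactive NAb as the leading immunogenicity safety outcome: Section 4.6.5.5.4 ties the immunogenicity events of special interest to treatment-emergent ADA associated with severe or serious hypersensitivity or injection site reactions.

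The conclusion rests on two assumptions: that the similar-terminology sentence carries the drug-tolerance rule to Tiers 2b and 2c, and that nothing in Figure GPHM.4.1 rules out drug interference there. The first is the natural reading. The second can be checked quickly against the figure and the assay validation.

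**What to change.** Split the first row of each block in Table GPHM.4.9. For Tier 2b (2c) Not Detected:

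- Tirzepatide below the Tier 2b (2c) tolerance limit, or missing: Not Present.
- Tirzepatide at or above that limit, with Tier 4a (4b) Not Detected and drug below the Tier 4a (4b) limit: Not Present.
- Tirzepatide at or above the Tier 2b (2c) limit, otherwise: Inconclusive.

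In every row, state whether the tolerance limit is that of the Tier 2 or the Tier 4 assay. If the sponsor has evidence that drug cannot mask Tiers 2b and 2c at study concentrations, a footnote saying so would serve instead of the split.

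The cost is a table edit and a small derivation change, with no new samples or assays. The downside is that a few TE ADA+ participants may move from NAb-negative to NAb-Inconclusive. If tolerance is never reached, no label changes.
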